**Background**

Maintaining tight blood glucose control following surgery is imperative to reducing infections and neurologic dysfunction. This requires frequent blood sampling while in the intensive care unit, leading to increased waste of blood and utilizing time and resources to collect samples and wait for results. Additionally, when on the regular floors, frequent point of care fingersticks for glucose levels are needed for therapeutic intervention.

Continuous glucose monitoring systems (CGMS) are now available for ambulatory use in patients with diabetes. The potential of using such a system in the hospital, including during the postoperative critical care setting and upon transfer to the regular floor, may reduce personnel burden, produce rapid results, and decrease blood waste.

However, these systems have not yet been validated for hospital use.

**Objectives**

To assess the accuracy of the continuous glucose monitor Dexcom G6 (or similar device) on patients with hyperglycemia, with or without known diagnosis of diabetes, after cardiovascular surgery.

To calculate potential cost savings, time savings, and blood waste compared to current care (point of care glucose through blood gas)

## **Methods**

All patients following cardio-thoracic surgery are required to have tight control of blood glucose, thus requiring multiple blood draws as part of the Surgical Care Improvement Project (SCIP).

### **Patients**

Patients will be identified and consented preoperatively

#### Inclusion criteria for consenting patients:

Age 18 years old and above

Planned Cardiovascular surgery

Planned admission to Cleveland Clinic Main Campus J5 or J6 or Q5 cardiovascular ICU (CVICU) post-operatively

With or without known diabetes (as 75% of patients entering the CVICU have hyperglycemia requiring intravenous insulin infusion)

If with known diagnosis of diabetes, diabetes can be type 1, type 2, or secondary (such as due to glucocorticoids or pancreatitis)

#### Exclusion criteria:

Allergy to the material of the CGMS or the adhesive to be used

Skin conditions precluding the use of the CGMS

Pregnancy

Other conditions that the investigators deem inappropriate for the study

#### Consent:

Consent will be performed pre-operatively at the TCI (To Come In) unit.

#### Procedure:

Dexcom G6 has a sensor (see photo below) that goes underneath the skin to sense interstitial glucose.

It is attached to a transmitter.

The third component is a receiver. The receiver has to be within 10-15 feet from the patient. We will place this in a well-marked pouch/bag.

In the photo below, the purple is the sensor and the gray oval on top of it is the transmitter. The sensor is inserted first, then the transmitter is attached to it.

The sensor/transmitter will be applied pre-operatively in the preop holding area or in the operating room (before anesthesia induction) to the upper outer arm by a physician, nurse, nurse practitioner or physician's assistant. The insertion area can be cleaned with alcohol or betadine.

The glucose readings on the device will not be visible to the ICU/regular floor staff nor the patients.

At the end of 10 days or upon discharge from the hospital, which ever comes first, the sensor/transmitter will be removed.

Time-stamped data from the CGMS software will be compared with the correlated ABG or venous of Accu-check Inform II glucose reading

The data transmission occurs via Blue-Tooth from sensor to the receiver.

The data have do be downloaded within 2 weeks.

The sensor has an adhesive so that it can stick to the skin. Skin Tac can be used to increase the adhesion to the skin. An adhesive overpatch specifically coming from/approved by Dexcom can be used over the sensor as needed to increase adhesion. NOTE: OpSite or Tegaderm CANNOT be used over the sensor as this will decrease reliability.

#### Sanitation

We requested for enough sensors and transmitters for 30 patients.

Should the transmitters fall short for some reason, they can be cleansed with bleach or alcohol

The sensors can only be used for one person each.

The receivers will come with sterile shields which will be changed in-between patients.

#### **Safety:**

The CGMS will be inserted on the outer arm after the site is cleaned. The insertion site will be inspected daily for signs of infection, or of allergy from the sensor, adhesive, or overpatch.

#### **Study Design**

This is a prospective longitudinal study to study the agreement between a novel continuous glucose monitoring system (CGMS) versus current blood glucose monitoring. Subjects in this study will have their blood glucose measured regularly every 1-3 hours with current methods in the CVICU, and by point of care glucose using the Accuchek Inform II on the regular floors, and the CGMS at the same time will be captured. Subjects will have measurements taken throughout their stay in the CVICU and on the regular floors. Agreement and correlation between systems will be calculated, and error will be classified using the Surveillance Error grid. The proportion of errors of at least moderate risk will be calculated.

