#### **Sample Size**

Sample size calculations were performed based on the precision of the moderate error rate as based on the surveillance error grid calculations. Given the goal to estimate the error rate to within 5% based on 95% confidence intervals, assuming 10 samples per patient and a moderate intraclass correlation coefficient (ICC) of 0.3, if the observed error rate is 5%, then 28 subjects (at least 271 paired samples) will be required to achieve this level of precision. Note that if you wish to estimate these levels with this precision for subgroups of your population, each subgroup will need to have this many subjects. Table 1 shows the number of samples required for different levels of precision and error rates under similar assumptions. Sample size calculations were performed using the online calculator by Dhand, N. K., & Khatkar, M. S. (2014).

**Table 1.** Samples required to achieve precision as described assuming 95% confidence, an ICC of 0.3, and 10 paired samples per subject. Number is subjects would be the number below divided by 10.

Error Rate	Absolute precision							
	0.03	0.04	0.05	0.06	0.07	0.08	0.09	0.10
20%	2527	1422	910	632	465	356	281	228
15%	2014	1133	725	504	370	284	224	182
10%	1422	800	512	356	262	200	158	128
5%	751	422	271	188	138	106	84	68

Primary outcome:

To address accuracy, glucose readings obtained from the CGMS will be compared with

- 1) blood glucose from the arterial blood gas (ABG) or peripheral/central venous catheter if arterial catheter not in use (standard of care in CVICU) while patients are in the CVICU
- 2) fingerstick point of care (POC) glucose when patients are on the regular floors

Other outcomes:

The following can be derived based on the average length of stay (LOS) of the study patients in the CVICU and the regular floors (current average of 24-36 hours, and a total hospital LOS of 4-5 days)

Cost savings: cost of CGMS device including sensor, transmitter versus cost of doing an ABG to obtain glucose levels (CVICU stay), and versus the cost of Accu-check Inform II meter, test strips, and lancets

Time savings: time it takes to perform and time it takes to have results based on an ABG or fingerstick POC on Accu-check Inform II

Blood waste: blood sample amount for an ABG or fingerstick POC on Accu-check Inform II

Variables:

Age

Gender

Race

Weight

Height

BMI

Systolic blood pressures

Diastolic blood pressures

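### No planned output counts reference tests or patients without a contemporaneous CGMS reading, and the savings outcomes make no deduction for them

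*Combined protocol and SAP*

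**What the plan says.** The Study Design section gives the planned outputs: "Agreement and correlation between systems will be calculated, and error will be classified using the Surveillance Error grid". Statistical Methods makes them specific: a repeated-measures concordance correlation, a repeated-measures correlation, error-grid classes and the rate of moderate-or-worse errors, each with a 95% confidence interval that allows for clustering. The Sample Size section is also written in pairs: "if the observed error rate is 5%, then 28 subjects (at least 271 paired samples) will be required to achieve this level of precision".

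The Data section says that the device reads every 5 minutes and that the reading nearest in time to each blood test is used. It sets no maximum gap and does not say what happens when no reading exists.

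The Procedure section acknowledges several ways to lose data. The sensor goes on before surgery and stays until discharge or day 10; "The receiver has to be within 10-15 feet from the patient"; adhesion aids are allowed; and there is a two-week limit on download.

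On savings, the list of other outcomes says: "The following can be derived based on the average length of stay (LOS) of the study patients in the CVICU and the regular floors". It mentions no adjustment for tests at which the CGMS gave no value.

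**The concern.** All the accuracy outputs are conditional on a pair existing. A reference test with no CGMS reading at that time is handled in one of two ways, and the plan does not say which. Under a literal nearest-reading rule it is paired with a value from before or after the gap, so unavailability is mixed into the accuracy figure. Under an unstated window it is dropped. A patient with no readings at all disappears under both. In no case does the report say how often the device had a value when one was needed.

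This bears on what the study is for. The Background section motivates it by possible hospital use that would spare staff time and blood, and adds: "However, these systems have not yet been validated for hospital use". The second objective is potential savings. A blood test is saved only if the CGMS had a value to put in its place, so savings built on length of stay alone credit the device with tests that it could not have replaced.

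**Working it through.** **Step 1: the plan's own figure.** Inputs from the Sample Size section: 95% confidence, half-width d = 0.05, error rate p = 0.05, and "assuming 10 samples per patient and a moderate intraclass correlation coefficient (ICC) of 0.3".

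- Design effect: 1 + (10 − 1) × 0.3 = 3.7.
- Pairs: 1.96² × 0.05 × 0.95 / 0.05² × 3.7 = 72.99 × 3.7 = 270.1, rounded up to 271.
- Subjects: 271 / 10 = 27.1, rounded up to 28.

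The stated 271 pairs and 28 subjects reproduce, as do all 32 cells of Table 1. The sample size arithmetic is correct, but it counts pairs only.

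**Step 2: would the pair target expose missing readings?** Tests every 1–3 hours (Study Design) over 24–36 hours (other outcomes, read here as the CVICU stay) give 24/3 = 8 to 36/1 = 36 CVICU tests per patient. For 28 patients that is 224 to 1,008 tests, before any floor tests.

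- At 1,008 tests, 271 pairs are reached with 1 − 271/1,008 = 73% of CVICU tests unpaired.
- At one test every 2 hours over 30 hours (15 × 28 = 420 tests), they are reached with 1 − 271/420 = 35% unpaired.

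So the target can be met while a large share of tests has no reading.

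**Step 3: would the confidence interval expose it?** With 28 patients, m pairs each and p = 0.05, the half-width is 1.96 × √{0.0475 × [1 + (m − 1) × 0.3] / (28m)}.

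- m = 10: 4.9 percentage points.
- m = 5: 5.35 percentage points.

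Losing half the pairs widens the interval by less than half a point, so precision is not a warning sign either.

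**Step 4: possible size.** The documents give no share of tests without a reading. Let f be that share (assumed), let tests without a contemporaneous reading be left unpaired, and let the error rate among pairs be the planning value of 5%.

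| f (assumed) | Reading present, no moderate-or-worse error: 0.95 × (1 − f) | No reading, or such an error: f + 0.05 × (1 − f) | Overstatement of gross blood and time savings: 1/(1 − f) |
|---|---|---|---|
| 5% | 90.25% | 9.75% | 1.05 |
| 10% | 85.5% | 14.5% | 1.11 |
| 20% | 76.0% | 24.0% | 1.25 |
| 30% | 66.5% | 33.5% | 1.43 |

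**Step 5: net cost behaves differently.** With N tests at cost c each and device cost D, the saving is Nc − D if every test is replaced and N(1 − f)c − D if a share f is not. The ratio of the two equals 1/(1 − f) only when D = 0. With D above zero and the corrected saving still positive, the ratio is larger. The documents give neither c nor D, so no figure can be stated.

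**Step 6: the nearest-reading rule.** A working sensor that reads every 5 minutes always has a reading within 2.5 minutes of a test. Without a maximum gap, a test in the middle of a two-hour signal loss (an illustration) would be paired with a value one hour away. Such a pair measures glucose change over that hour as well as sensor error.

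**The case against.** The strongest reply is that the first objective is accuracy, and accuracy given a reading is a legitimate answer to it. Availability is a separate quantity. That stands: the planned accuracy measures are not wrong in themselves. But the second objective concerns savings, and those cannot be computed properly without availability.

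Four stronger inferences are tempting, and the documents do not support them.

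- A reader might infer that the plan would report the same 5% error rate however often the sensor failed, so that a poor device would look fit for hospital use. That needs a pairing window that the plan lacks and an unchanged error rate among the remaining pairs. Stale pairs could push the reported error up instead.
- A reader might infer that failures gather in the early postoperative hours and so bias the remaining pairs in the device's favour. The documents give neither the timing of failures nor a direction of bias.
- A reader might infer a decision rule for replacing blood tests. There is none, and no acceptance threshold; hospital use is motivation only.
- A reader might apply the 1.05 to 1.43 factor to cost. Step 5 shows why it does not carry over.

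It is also fair to say that a missing value is not always the device's fault. Staff cannot see the readings, and a receiver left out of range or a missed download is study logistics. This affects how availability is interpreted, but it is no reason to leave it out.

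**Conclusion.** The omission is confirmed. Every accuracy output is conditional on a paired CGMS value, no output counts tests or patients without a contemporaneous one, and the savings outcomes carry no deduction for such tests. The report therefore could not say how often the CGMS had a usable value at the time of a blood test.

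The size is illustrative. For an assumed 5% to 30% of tests without a reading, and a 5% error rate among pairs, the share with a usable value is 90% down to 67%, and gross blood and time savings are overstated 1.05 to 1.43 times. The savings figure further assumes that every test during the stay is credited as replaced; the plan gives no formula but mentions no exception. The effect on net cost cannot be sized, and the effect on the reported error rate could go in either direction. The sample size calculation is unaffected.

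**What to change.** 1. **Statistical Methods and Data:** define a contemporaneous reading by a stated window, for example within 5 minutes to match the device's reading interval, and compute the accuracy outputs on those pairs.
2. **Statistical Methods:** among all patients with a sensor inserted, report by setting (CVICU, floor) the number and percentage of reference tests with a reading in the window, with a cluster-adjusted 95% confidence interval, and the number of patients with no usable readings.
3. **Secondary figure:** report the percentage of all reference tests that had a contemporaneous CGMS value and no moderate-or-worse error. State alongside it that missing values may reflect study logistics as well as device failure.
4. **Other outcomes:** count as saved only reference tests with a contemporaneous CGMS value, and keep the device cost in full.

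Reference times and the 5-minute export are already collected, so the cost is analysis wording, slightly more analysis work, and a less favourable usability and savings figure. Survival of the first sensor to discharge or day 10 would be informative, but it needs records of detachment and replacement that are not in the variable list. It should be optional.

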#### **Subject compensation**

There is no subject compensation for this study.

#### **Statistical Methods**

Subject characteristics including demographics, comorbidities and baseline disease severity will be summarized using means and standard deviations for continuous measures and frequencies and percentages for categorical factors. To evaluate agreement between methods, concordance correlation coefficients will be calculated, using the method that adjusts for repeated measures as described by King et al. (2007) and implemented in software by Carrasco et al. (2013). Analysis will be performed overall, and then stratifying by type of current measure, if the type of measurement varies across settings. Correlations will be calculated using the methods described by Bland and Altman (1995) and implemented by Bakdash and Marusich (2017). Differences will also be evaluated for errors according to the Surveillance Error Grid (Klonoff et al, 2014). Rates of moderate or more severe errors will be calculated. For each measure above, 95% confidence intervals will be calculated, accounting for the clustering within subject.. Analyses will be performed using SAS software (version 9.4; Cary, NC) and R software (version 3.5; Vienna Austria).

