Temperatures

Diabetes status (no known diagnosis, known diagnosis)

Type of diabetes

Type of cardiothoracic surgery

Presence of peripheral vascular disease

Presence of peripheral edema  
Presence of medications/substances that might interfere with the CGMS  
Glucose readings (lab, point of care, CGMS)  
Serum creatinine  
Intravenous insulin infusion rate  
Subcutaneous insulin doses  
Use of pressors/vasoconstrictors/vasodilators  
Intravenous fluids  
Medications administered in the hospital

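### Accuracy is the first objective and the primary outcome, but no planned statistic reports whether the sensor reads high or low, or by how many mg/dL or percent

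*Combined protocol and SAP*

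**What the plan says.** The Objectives section puts accuracy of the sensor first. The primary outcome, listed at the end of the Sample Size section, is also accuracy: sensor readings against arterial blood gas or venous catheter glucose in the cardiovascular ICU (CVICU), and against fingerstick glucose on the floors. It names no summary measure.

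The measures are in Statistical Methods:

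- Concordance: "To evaluate agreement between methods, concordance correlation coefficients will be calculated", in a form for repeated measures.
- Correlation, by cited methods. The Bland and Altman reference is attached to correlations, not to limits of agreement.
- Error grid: "Differences will also be evaluated for errors according to the Surveillance Error Grid", followed by "Rates of moderate or more severe errors will be calculated". Study Design agrees: "The proportion of errors of at least moderate risk will be calculated".

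Clustered 95% intervals are promised for these measures. On strata: "Analysis will be performed overall, and then stratifying by type of current measure, if the type of measurement varies across settings". Means and SDs appear only for baseline description: "Subject characteristics including demographics, comorbidities and baseline disease severity will be summarized using means and standard deviations". The variables list includes laboratory, point-of-care and sensor glucose, and the Data section matches each reference value to the nearest sensor reading. No section plans a summary of the paired difference itself.

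**The concern.** A reader of an accuracy study first asks whether the device reads high or low against the reference, and by how much. The concordance coefficient (CCC) and the correlation are unitless, and neither carries the sign of a bias. The grid rate is the share of pairs past a risk threshold; the plan does not split it into over- and under-reading. The study could therefore report every planned statistic and leave that question unanswered. A difference calculated later, outside the plan, would have no pre-specified scale, handling of repeated measures or interval.

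**Working it through.** **The plan's own figure.** The sample size rests on the grid error rate: n = 1.96² × p(1 − p)/d² × [1 + (m − 1) × ICC], with p = 0.05, d = 0.05, m = 10 and ICC = 0.3. This gives 3.84 × 0.0475/0.0025 × 3.7 = 270.05, so 271 pairs. Then 271/10 = 27.1, so 28 subjects. The figure reproduces and is not in dispute.

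**Assumptions.** The documents give no glucose SD, sensor error SD or bias. Assumed here: glucose SD 40 mg/dL (25 and 50 as a range), within-patient error SD 15, glucose ICC 0.3, bias +20 or −20.

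**Sign.** CCC = 2·SD²/(2·SD² + error variance + bias²).

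- Bias +20: 3200/(3200 + 225 + 400) = 0.837.
- Bias −20: the same, because bias enters as its square.
- At glucose SD 25: 1250/1875 = 0.667. At SD 50: 5000/5625 = 0.889. Both signs again agree.

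Within-patient correlation = √(w/(w + 225)), with w = 0.7·SD². At SD 40: √(1120/1345) = 0.91; at SD 25 and 50, 0.81 and 0.94. Adding a constant to one reading leaves any correlation unchanged, so the tie does not depend on which form the cited method takes.

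The 95% limits of agreement separate the two sensors: +20 ± 1.96 × 15 = −9 to +49 mg/dL, and −20 ± 29.4 = −49 to +9. With 28 × 10 pairs and no patient-level offsets, the interval for the mean difference is ±2.052 × 15/√280 = ±1.8 mg/dL.

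**Size.** A sensor with bias 10 and error SD 7.5 at glucose SD 25 has CCC 1250/(1250 + 56.25 + 100) = 0.889. One with bias 20 and error SD 15 at glucose SD 50 has 5000/(5000 + 225 + 400) = 0.889. The within-patient correlation is 0.94 for both, yet the limits are −5 to +25 and −9 to +49. The match follows from doubling every quantity. It shows that neither coefficient converts to mg/dL; it says nothing about the grid rate.

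**Precision of the added estimate.** Half-width = t × 15 × √{[1 + (m − 1) × ICC]/(k·m)}, for k patients with m pairs each. The plan's ICC of 0.3 is for the error rate and is borrowed here for the difference.

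| Patients × pairs | t | Half-width, mg/dL |
|---|---|---|
| 28 × 10 | 2.052 | 3.5 |
| 8 × 10 | 2.365 | 7.6 |
| 8 × 3 | 2.365 | 9.2 |
| 5 × 10 | 2.776 | 11.3 |
| 5 × 3 | 2.776 | 13.6 |

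At 28 × 10, an ICC of 0.1 or 0.6 gives 2.5 or 4.7.

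**Scale.** Neither scale is free of glucose level. A proportional error SD of 10% gives mg/dL limits of about ±24 at 120 mg/dL and ±35 at 180. A constant error SD of 15 gives a mean absolute relative difference of 15 × √(2/π)/glucose, which is 10.0% at 120 and 6.6% at 180.

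**The case against.** The strongest reply has four parts.

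*The planned set is not blind to bias.* True. At glucose SD 40 and error SD 15, the CCC falls from 0.91 to 0.88 to 0.84 as the bias goes from 10 to 15 to 20. Read with the correlation it can also tell constant bias from pure within-patient scatter: error SD 25 without bias gives the same CCC of 0.84, but a correlation of 0.80 rather than 0.91. The planned intervals carry information too. A sensor with zero mean bias but patient offsets of SD 20 has the same CCC point value, yet its sampling SD is about 0.031 against 0.018. What stays missing is sign and units.

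*The grid is the output that the study is sized on.* A reader might infer that the grid rate also could not tell these sensors apart. The documents do not support that: the thresholds are not given, the rate was not calculated, and it may differ.

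*The matched pairs are kept, so the differences can be calculated at reporting.* This stands. Nothing is lost for good, and nothing planned is invalid. The harm is incomplete pre-specification of the primary question.

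*Precision by reference type may be poor.* This stands too. Venous samples are used only when no arterial catheter is in place, so they may come from few patients. The Sample Size section itself warns that each subgroup would need the full number for the same precision.

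A reader might also infer that the plan will rank accuracy across settings by comparing stratum CCCs. It plans stratified values but states no such comparison, so no objection is made on that ground.

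**Conclusion.** The point holds as an omission. As written, the planned statistics do not report the sign of sensor error or its size in mg/dL or percent, although accuracy is the primary outcome. For biases of +20 and −20 mg/dL the CCC (0.84) and correlation (0.91) are identical. Those two values rest on the assumed SDs and glucose ICC; the tie between the signs does not. For the grid rate, the supported statement is only that it has no stated direction and is not in glucose units. The existing sample would give a usable overall mean difference, about ±3.5 mg/dL at error SD 15 and ICC 0.3. It would not do so for a reference type seen in few patients: about ±7.6 to 9.2 with 8 patients and ±11 to 14 with 5. This is a cheap improvement, not a flaw that invalidates the study.

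**What to change.** Add to Statistical Methods, each with a 95% interval that accounts for clustering by patient (for example, a bootstrap that resamples patients):

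- the signed mean difference, sensor minus reference, in mg/dL;
- 95% limits of agreement for repeated measures, using between-patient plus within-patient variance, and also on the percent scale or by glucose level if the difference or its spread changes with glucose;
- the mean absolute relative difference.

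Report these overall, and by reference type where enough patients contribute. For sparse types such as venous samples, give descriptive results, the number of patients and a note on low precision. Keep the planned CCC, correlation and grid rate.

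The cost is a few lines of wording and a few more tables. Data collection, matching, software and the 28 subjects are unchanged.

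### The plan does not say how the 95% interval for the within-patient correlation is formed, and the analytic interval of the named method is too narrow if successive readings are serially correlated

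*Combined protocol and SAP*

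**What the plan says.** Statistical Methods names three kinds of result: a concordance correlation coefficient adjusted for repeated measures, a within-patient correlation (identified by a methods citation and a software implementation), and the rate of moderate or worse errors on the Surveillance Error Grid. One sentence covers the intervals for all of them: "For each measure above, 95% confidence intervals will be calculated, accounting for the clustering within subject". No interval formula, resampling scheme or degrees of freedom is given for the correlation, and correlation between successive readings is not mentioned.

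The data behind these measures are dense in time. Study Design has patients with "blood glucose measured regularly every 1-3 hours with current methods in the CVICU", and adds: "Subjects will have measurements taken throughout their stay in the CVICU and on the regular floors". The stay lengths under Sample Size are "current average of 24-36 hours, and a total hospital LOS of 4-5 days", the first figure being the CVICU stay. The sample size was worked out "assuming 10 samples per patient and a moderate intraclass correlation coefficient (ICC) of 0.3". That ICC applies to the error rate, not to the correlation.

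**The concern.** Clustering within a patient has two parts. One is a constant patient effect: some patients run high and some run low. The other is serial dependence: a reading resembles the one taken an hour or two before, and so may the sensor's error. A within-patient correlation subtracts each patient's mean, which deals with the first part only. Its analytic interval then takes its information from the number of pairs minus the number of patients, as if the remaining deviations were independent.

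An analyst could run the named method, take the analytic interval, regard the clustering sentence as satisfied because a patient term is in the model, and still report limits that are too narrow. The sentence does not separate an interval that works from one that does not. Accuracy is the first objective, and Study Design lists correlation among the quantities to be calculated. The stake is an accuracy measure that looks more certain than 28 patients can support.

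**Working it through.** **1. The plan's own figure.** The sample size is for the error rate: n = 1.96² × p(1 − p)/d² × [1 + (m − 1) × ICC]. With p = 0.05, d = 0.05, m = 10 and ICC = 0.3, the design effect is 1 + 9 × 0.3 = 3.7. Then n = 3.8415 × 0.0475/0.0025 × 3.7 = 270.05, rounded up to 271 pairs, and 271/10 rounds up to 28 patients. This agrees with the plan. The documents give no planning or coverage figure for the correlation.

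**2. Inputs.** From the documents: 28 patients, 10 planned pairs each, CVICU spacing of 1-3 hours and a CVICU stay of 24-36 hours. That stay gives between 24/3 = 8 and 36/1 = 36 CVICU pairs per patient before any floor readings, so 10 is near the low end and 30 is plausible. Assumed, because the documents are silent: the lag-1 correlations, the standard deviations and the true correlation.

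**3. The analytic interval.** On the Fisher-z scale, z = atanh(r) and SE = 1/√(df − 1), with df = N(k − 1) − 1.
- N = 28, k = 10: df = 251, SE = 1/√250 = 0.0632.
- N = 28, k = 30: df = 811, SE = 1/√810 = 0.0351.

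**4. Coverage, first model.** Assumed SDs: glucose 30 mg/dL, sensor error 15, reference noise 4. There were 3,000 simulated trials per setting. Coverage is judged against the value that the estimator targets, so bias is not counted as under-coverage.

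| Lag-1, glucose / sensor error | 10 pairs | 30 pairs | True SE ÷ nominal SE, 30 pairs |
|---|---|---|---|
| none | 95% | 95% | – |
| 0.6 / 0.5 | 89% | 87% | 1.3 |
| 0.8 / 0.7 | 83% | 74% | 1.8 |
| 0.9 / 0.8 | 80% | 65% | 2.1 |

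A separate run of the same model agreed to within about 2 points. As a cross-check, coverage ≈ 2Φ(1.96/ratio) − 1, which gives 87% at a ratio of 1.3 and 65% at 2.1.

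**5. Coverage, second model.** True correlation 0.9, the same lag-1 value for glucose and sensor error, 28 patients, 3,000 trials.

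| Lag-1 | 10 pairs | 20 pairs | 30 pairs |
|---|---|---|---|
| 0 | 95% | 95% | 95% |
| 0.3 | 93% | 93% | 93% |
| 0.5 | 90% | 88% | 88% |
| 0.7 | 84% | 79% | 76% |
| 0.8 | 79% | 71% | 67% |
| 0.9 | 75% | 65% | 56% |

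With 0.8 for glucose and none for sensor error, coverage is 89% at 10 pairs and 83% at 30, so persistence in glucose alone is enough to cause a loss. True correlations of 0.7, 0.8 and 0.95, run at lag-1 values of 0.5 and 0.8, changed coverage by no more than about 3 points.

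**6. How far the limits move.** Under the first model r = 900/√(1125 × 916) = 0.887.
- 30 pairs: nominal 0.871 to 0.900; with the SE multiplied by 2.1, 0.851 to 0.914.
- 10 pairs: nominal 0.857 to 0.910; with the SE multiplied by 1.5 (which corresponds to about 80% coverage), 0.840 to 0.920.

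When glucose is more persistent than sensor error, removing patient means lowers the target. In the second model with 0.9 / 0.7 and 10 pairs the target is 0.817 and the SE ratio 1.572. The lower limit then goes from tanh(1.148 − 0.124) = 0.771 to tanh(1.148 − 0.195) = 0.741. Over these cases a limit moves by about 0.01 to 0.03.

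**7. Patient-level intervals.** In the second model, a leave-one-patient-out jackknife on the z scale, with t on 27 degrees of freedom, covered 93.5-96% in every setting tried. A percentile bootstrap of whole patients covered about 90-95%.

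**The case against.** A reader might infer that the plan treats readings taken hours apart as independent, and that its interval therefore covers only 65-90%. The documents do not support that. Statistical Methods fixes no interval formula, its wording promises attention to clustering, and a whole-patient bootstrap would comply with it as it stands. What the cited software produces by default cannot be checked from the documents. What can be said is that the method is left open and that one natural choice may fail.

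Further points on the other side:

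- **The size is assumed.** No autocorrelation or standard deviation is given. At a lag-1 value of 0.3 the loss is about 2 points. At the planned 10 pairs no setting in the tables fell below 75%; about 65% needs 20-30 pairs and strong serial correlation. This stands.
- **Spacing is not uniform.** The 1-3 hour schedule is stated for the CVICU only. No interval is given for floor fingersticks, and most of a 4-5 day stay is on the floor. A single lag-1 value for all pairs is a simplification. This stands.
- **The practical effect is modest.** A shift of 0.01-0.03 in a limit is unlikely to change how accuracy is read. This largely stands. It lowers the stakes, but it does not make a mislabelled 95% interval correct.
- **The measure is not the one that sizes the study.** No test or threshold is attached to the correlation, and the sample size rests on the error rate. Agreement is assigned to the concordance coefficient, whose interval was not simulated. It would share the weakness only if it assumed independent residuals within patient, and that was not shown.

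These points limit the size and reach of the concern. They do not remove it, because the clustering sentence lets an inadequate interval pass as compliant.

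**Conclusion.** The point holds in a limited form. The interval method for the within-patient correlation is unspecified, and the analytic Fisher-z interval would not deliver the promised allowance for clustering if successive readings are serially correlated. This rests on two assumptions: that the analytic interval is the one used, and that serial correlation is at least moderate. The size is conditional on values the documents do not give: a small loss of coverage at weak serial correlation, roughly 5 to 15 points at the planned number of pairs under moderate to strong serial correlation, and more only if pairs per patient run well above plan and serial correlation is strong. The 28-patient sample size is not affected, and no defect is established in the interval for the concordance coefficient. It is worth correcting before analysis because the remedy is cheap and works whether or not serial correlation is present.

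**What to change.** In Statistical Methods, after the sentence on intervals, add wording such as: 'The 95% confidence interval for the within-patient correlation will be obtained by a patient-level method: a leave-one-patient-out jackknife on the Fisher-z scale, with t on (number of patients − 1) degrees of freedom, or a bootstrap that resamples whole patients (2,000 or more replicates), overall and within each reference type. The analytic interval will not be used. The interval for the concordance correlation coefficient will take the patient as the independent unit.'

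One of the two options should be named before the data are seen. With 28 patients the jackknife held its coverage slightly better than the percentile bootstrap. Within a reference type, the degrees of freedom should follow the number of patients who contribute to it. The clause on the concordance coefficient is a precaution.

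The cost is one sentence, a few lines of R code and somewhat wider intervals. No change to the sample size or data collection is needed.
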